The proposed intracranial stimulation parameters are both historically common and proven safe in epileptic populations. Stimulation will be current-regulated and charge-balanced, with biphasic rectangular pulses. The anticipated electrode impedence is 1-4 k Ω . Stimulation will be bipolar, with the electrodes placed 1.5 mm apart (surface area, 0.059 cm). Prior to testing, current amplitude will be increased in a stepwise fashion in order to identify the threshold for afterdischarge (anticipated range 0.2-2 mA), and then decreased by 25% for the maximum amplitude for the duration of testing. The subjects will be blinded to stimulation condition. These parameters are similar to intracranial stimulation parameters used in other ongoing translational research protocols at Emory University Hospital over many years^{44,45}.

Pre-stimulation threshold testing:

Before the session, the epilepsy monitoring staff and patient will be consulted to determine if the patient has had any clinical seizures in the previous 2 hours. If the patient has had a clinical seizure in the previous 2 hours, then the experiment will be delayed until a 2 hour,

seizure-free period has been met. For each session, we will ask the patient for verbal consent to testing. During the entirety of all sessions, a study neurologist, clinical neurophysiologist, or neurosurgeon will monitor the subject and view the real-time EEG for afterdischarges. If any afterdischarges are observed, the protocol will be immediately halted and the patient assessed. Once afterdischarges have stopped, stimulation current will be decreased by 25-30% and testing will resume. If afterdischarges occur again, all testing will be aborted on the patient. If at any time clinical seizures are elicited during stimulation, all testing of that patient will be aborted.

The goal of the first session will be to establish the range of safe stimulation parameters that can be tested in subsequent parameter sweeps. The procedure for safety threshold testing is as follows:

- Seven stimulation frequency pulse-width combinations will be tested:
 - o 2 Hz, 450 μs
 - o 7 Hz, 450 μs
 - o 50 Hz, 450 us
 - o 90 Hz, 100 μs
 - o 90 Hz, 450 us
 - o 125 Hz, 100 μs
 - o 125 Hz, 450 us

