- Each frequency/pulse width combination will be tested at 0.25 mA, and incremented by 0.25 mA until the patient reports adverse side-effects, undesired changes are observed in the real-time LFP, or 3.0 mA is reached. This limits the number of tests to 5 frequency/pulse width combinations at 12 current amplitudes, for a maximum total of 60 stimulation patterns to be evaluated for safety.
- The test of each stimulation pattern will consist of 5 seconds of stimulation, followed by 15 seconds of washout (20s total), repeated 3 times, for a total of 60 seconds per stimulation pattern. For lower frequencies, a longer stimulation train may be administered to increase likelihood of observing effects (e.g. 10 15 sec). During memory tasks, stimulation trains up to 15 minutes will be used to provide sufficient time to observe any temporary effects of stimulation on memory tasks as has been previously reported.
- The total test time will be approximately 60 minutes.
- For the following parameter search, the maximum current threshold for each frequency/pulse width combination will be set to 80% of the current that induced patient-reported side-effects or undesired changes to the LFP.
- The clinician conducting the threshold testing is at liberty to test additional safe parameters, under the current safety limit, at their discretion.
- Lower current limits may be determined based on the neurologist's discretion given what is known about the patient's epilepsy.

Parameter search:

During subsequent sessions, the focus will be on collecting the data necessary to evaluate the effect of different stimulation patterns (combinations of stimulation parameters) on the neural signal. The default approach will be to conduct a randomized sweep of stimulation patterns. Randomized sweeps are typically superior to the more traditional grid search

approach, as a more diverse array of stimulation patterns can be tested. While a grid search lends itself to more classical statistical analysis (e.g. ANOVA), we've shown that the data collected using a random search can be analyzed using a non-parametric Gaussian process (GP) model. The stimulation parameter space will be discretized as:

- Current 0.1-3.5* mA with 0.1 mA increments (35 values)
- Frequency 2-125 Hz with 1 Hz increments (124 values)
- Pulse width 100-450† μs with 10 μs increments (35 values)
- * The maximum current will be derived based on the results of the initial threshold testing

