The stimulation parameters that we will use have been informed by our previous human studies our nonhuman primate data and fall within the range of typically used clinical stimulation parameters. When stimulation of the brain region within which seizures arise is performed, occasional epileptiform discharges can be seen. These are not seizures, but single events lasting < 200 ms that are the sign of increased excitability of the brain. These after-discharges can warn that seizure may occur with more intense stimulation. To avoid seizures, a neurologist will always be performing the stimulation and watching the real time EEG for these discharges. If a particular current intensity causes after-discharges, the current intensity of subsequent stimulations will be reduced.

Electrical stimulation of brain, using our technique and stimulus parameters, has minimal risk. The main risk is that stimulation might trigger a seizure, but this is uncommon given guidance by study staff who are neurologists trained in human electrophysiology and brain stimulation, and, with our stimulation parameters (careful attention to current density and emphasis of low-frequency stimulation; avoidance or appropriate decrease of current density and use of only low frequency stimulation in the hippocampal formation).

In the present study, current density will be kept below the typical safety limit of SEEG stimulation of 30 μ C/cm²/phase (thirty micro-Coulombs per square centimeter per phase), calculated based on current delivered per second and electrode surface area [8]. Stimulation will be graded, starting at very low current density then gradually increased.

During stimulation, the EEG will be observed by a trained neurologist physician with experience with reading intracranial EEG. If epileptiform discharges appear we will stop the stimulation run. If these continue we will use the ictal disrupt feature. We will then decrease the current and continue, but typically we will already have useful data at a lower current intensity. In the unlikely event that a seizure occurs, and becomes prolonged, lorazepam (1-2 mg IV) will be administered under the direction of a physician (there will always be a physician present), as per standard epilepsy monitoring unit protocol.

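### The abort rule does not say whether after-discharges that end a threshold ramp count toward it, and the safety overview omits the abort

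*Combined protocol and SAP*

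**What the plan says.** Three parts of the protocol deal with after-discharges.

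- **Intracranial stimulation protocol.** Before testing, current is stepped up "in order to identify the threshold for afterdischarge (anticipated range 0.2-2 mA), and then decreased by 25% for the maximum amplitude".
- **Pre-stimulation threshold testing, abort rule.** "During the entirety of all sessions, a study neurologist, clinical neurophysiologist, or neurosurgeon will monitor the subject and view the real-time EEG for afterdischarges". Any after-discharge halts the protocol while the patient is assessed. "Once afterdischarges have stopped, stimulation current will be decreased by 25-30% and testing will resume". Then: "If afterdischarges occur again, all testing will be aborted on the patient".
- **Pre-stimulation threshold testing, ramp.** "Seven stimulation frequency pulse-width combinations will be tested". Each starts at 0.25 mA and is "incremented by 0.25 mA until the patient reports adverse side-effects, undesired changes are observed in the real-time LFP, or 3.0 mA is reached". For the later parameter search, "the maximum current threshold for each frequency/pulse width combination will be set to 80% of the current that induced" the side-effect or LFP change. A closing bullet lets the neurologist set lower current limits in view of the patient's epilepsy.
- **Risks to Participants, General overview of stimulation safety considerations.** "If epileptiform discharges appear we will stop the stimulation run. If these continue we will use the ictal disrupt feature". The current is then lowered and stimulation goes on. This overview gives no abort and no limit on repeats.

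**The concern.** The abort rule treats a second after-discharge as a reason to end a patient's participation. The ramp treats an after-discharge as a possible endpoint, to be approached separately in each of seven combinations. The monitoring statement covers all sessions, so the threshold session is not exempt. The text does not say whether the count runs per patient, per session or per combination.

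Two bedside teams could therefore act in opposite ways, each with the protocol in hand. One would stop a patient in session 1, before the parameter sweep and the stimulated memory test. The other would finish all seven ramps and be open to the charge of ignoring a written safety abort. If the literal rule were applied, the patients lost would tend to be those with the lowest after-discharge thresholds, so the remaining data would come from less excitable hippocampi.

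**Working it through.** **1. The rules side by side.** An after-discharge is taken here to be an undesired LFP change; the protocol does not define that term.

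| Event | Abort rule | Ramp procedure | Safety overview |
|---|---|---|---|
| First after-discharge | Halt, assess, cut 25-30%, resume | Ends that ramp; ceiling at 80% | Stop run, lower current, continue |
| Second, at the reduced current | Abort all testing | Not addressed | Lower and continue |
| Second, in another combination | Abort if read literally; no abort if *again* means at the reduced current | Ends that ramp; its own ceiling | Lower and continue |

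The texts agree that the first event means stopping and using less current. They part on repeats.

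**2. Would the ramp reach the anticipated threshold?** The ramp has 3.0 / 0.25 = 12 steps. The lower end of the anticipated range, 0.2 mA, is passed at step 1, since 0.2 / 0.25 = 0.8. The upper end, 2 mA, is reached at step 2 / 0.25 = 8. The charge limit does not stop the ramp first: 3.0 mA x 450 µs = 1.35 µC, and 1.35 / 0.059 = 22.9 µC/cm² per phase, below 30 (the area is printed in cm and taken as cm²). Within the anticipated range, an after-discharge comes before the 3.0 mA cap unless a side-effect or another LFP change ends the ramp sooner.

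**3. How many events can the ramp meet?** Up to one per combination, so up to 7. A later bullet still counts 5 combinations (5 x 12 = 60 patterns, against 7 x 12 = 84 for the list). Either number exceeds the single event that the literal abort tolerates.

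**4. Does the reduction carry over?** Suppose the first after-discharge is at 2.0 mA. The cut gives 2.0 x 0.70 = 1.4 to 2.0 x 0.75 = 1.5 mA. The next combination starts at 0.25 mA and may rise to 3.0 mA, past the reduced level. Nothing says whether the cut limits it.

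**5. The two ceilings.** For a threshold of 0.2-2 mA, 75% gives 0.15-1.5 mA and 80% gives 0.16-1.6 mA. The gap is at most 0.1 mA.

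**6. Illustration only.** Let p be the chance that one ramp ends in an after-discharge. The documents do not give p. With independent ramps, P(2 or more of 7) = 1 - (1-p)^7 - 7p(1-p)^6.

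| Assumed p | Independent | Within-patient correlation 0.3 (assumed) |
|---|---|---|
| 0.05 | 4% | 9% |
| 0.10 | 15% | 18% |
| 0.20 | 42% | 35% |
| 0.30 | 67% | 51% |
| 0.50 | 94% | 77% |

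The spread shows that the outcome depends almost wholly on an unknown.

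**The case against.** The strongest reply is that the abort rule reads as a sequence: halt, reduce, resume, and abort if it happens again. The natural sense of *again* is then at the reduced current. On that reading each combination may have its own first after-discharge, the abort and the ramps fit together, and no patient need be lost by completing the ramps. This stands as a plausible reading, so a reader who infers that the instructions cannot all be followed goes too far. The text does not state that reading, however, and the safety overview would still lack the abort.

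Three further replies also have force.

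- The neurologist may set lower limits, so seven after-discharges are never required. That is a permission. It neither tells the team to act after a first event nor says how events are counted.
- The overview is a risk summary and does not countermand the abort. Following the stricter, specific rule breaches nothing in it. The defect there is an omission.
- The 75% and 80% ceilings are not a real conflict. The 80% also covers side-effects, and where both apply the lower satisfies both.

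**Conclusion.** The concern holds as an unresolved rule for repeated after-discharges. Read literally, one abort rule for all sessions can end a patient's testing during session 1 because of events that the ramp is designed to find. Read as recurrence after the reduction, the abort and the ramp are compatible, but the protocol leaves that choice to the bedside. This should be corrected; it does not depend on any assumed rate.

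The documents do not support several stronger inferences.

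- **A predicted loss of patients or of power.** The 4% to 94% range rests on an assumed p. The documents also do not say whether patients whose testing is aborted would be replaced, so no reduced sample size or detectable effect can be derived.
- **Seven after-discharges in every patient.** That would apply one anticipated range to combinations from 2 to 125 Hz and from 100 to 450 µs, and would ignore the other ways a ramp can end.
- **Unprotected patients.** A specialist watches the EEG throughout, and each text stops stimulation at the first event.

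**What to change.** 1. In Pre-stimulation threshold testing, state that an after-discharge ends the ramp for that combination, and that the abort applies if after-discharges recur after the 25-30% reduction. State the maximum number of ramp-ending after-discharges per patient before all testing stops. A maximum of 1 reproduces the literal rule; 7 is the most permissive. The choice is clinical. Because the change may relax the literal rule, submit it to the IRB and DSMB.
2. After an after-discharge, have the neurologist use the existing discretion to start or cap the remaining combinations at lower current.
3. Per combination, set the ceiling at 75% of the after-discharge current where an after-discharge set the limit, and keep 80% for side-effects or other LFP changes.
4. In the safety overview, make the instruction to lower the current and go on subject to the abort in Pre-stimulation threshold testing.

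The cost is wording in two sections and one submission. A few patients may stop earlier or be swept over a slightly lower current range.

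A larger redesign, raising all combinations together level by level under one common ceiling, is not needed. It would have to keep separate limits for combinations stopped by side-effects. It would also restrict patterns that tolerate more current and could bar the sweep for patients with the lowest thresholds.

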Title: Electrophysiological biomarkers during invasive monitoring of mesial temporal lobe epilepsy patients

Date: Sept/09/2021

NCT# NCT04710004

Emory IRB Biomedical Protocol Outline For Investigator-Initiated Studies

Title Page

Electrophysiological biomarkers during invasive monitoring of mesial temporal lobe epilepsy patients

Short study title: Electrophysiologic biomarkers in MTLE patients

Name, Title, and Department of Principal Investigator

[name], PhD

Professor, Department of Neurosurgery

Ph:
Emory University

Sponsor

[name], PhD

Professor, Department of Neurosurgery

Ph:
Emory University

External (non-Emory) Collaborators (if applicable)

• No external collaborators.

Protocol version number and version date

Version 2.0, September 9, 2021

Revision #	Version Date	Summary of Changes
2.0	September 9, 2021	Changes to the Intracranial Stimulation Protocol section (Study Design and Methods): (i) addition of 2 new stimulation frequency pulsewidth combinations for safety threshold testing; (ii) Addition of stimulation-trains of up to 15 minutes for use in revised memory testing protocol. Change to ADMES effects on memory (Study Design and Methods): (iii) Revisions to the memory testing procedure to include object recognition tasks after initial encoding and 15-minute distraction period along with continuous 15-minute neurostimulation-trains and ("Electric WADA").

Table of Contents

Study Summary	4
Objectives- The Primary Aim and Outcome Measures	4
Background	5
Study Endpoints	6
Study Design and Methods	6
Procedures Involved	13
Data and Specimen Banking	14
Sharing Results with Participants	14
Study Timelines	15
Inclusion and Exclusion Criteria	15
Vulnerable Populations	15
Local Number of Participants	15
Recruitment Methods	15
Withdrawal of Participants	16
Risks to Participants	16
Potential Benefits to Participants	18
Data Management and Confidentiality	19
Provisions to Monitor the Data to Ensure the Safety of Participants	19
Site Monitoring Plan	22
Provisions to Protect the Privacy Interests of Participants	22
Economic Burden to Patients	22
Consent Process	22
Setting	23
Resources Available	23
References	2.4

Study Summary

Study Title	Electrophysiological biomarkers during invasive
	monitoring of mesial temporal lobe epilepsy patients
Study Design	Nonrandomized interventional
Primary Objective	Identify biomarkers related to the precictal state;
	determine stimulation patterns that modify biomarkers

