- † The maximum pulse width is limited depending on the frequency

These three discretized parameters will be combined to produce input space consisting of a maximum 156,240 potential stimulation patterns, minus those that identified as unsafe by the initial threshold testing, and prohibited by the limitations of the hardware.

The random sweep will be conducted using 180 non-repeated stimulations consisting of 5 second of stimulation, followed by an average of 15 seconds of washout. For each stimulation, the duration of the washout will be selected from a uniform distribution on the interval [10 20] seconds. Data will be analyzed by measuring power spectral and timeseries features, and using computational tools to estimate biomarkers written in Matlab. This will be done offline following the session.

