We will schedule a time that is convenient for the patient to undergo testing, typically suggesting that a 1-2 -hour block of time is ideal. On the day of proposed testing, we will again check with the clinical team and patient that the originally proposed time and date is still acceptable.

Patient Instructions

General Instructions. The patient is asked to get comfortable and if they need to use the restroom or need anything to drink. The patient is asked to minimize head movement during the study, as well as to maintain wakefulness. During the majority of the sessions during which patient participation is not needed, they can watch television, read or talk to friends or family members that they permit to remain in the room. During stimulation, patient is continuously monitored clinically, as well as by EEG. If the patient notes anything they are to verbalize this or raise a hand. Stimulation is then immediately stopped

to discuss what was noted. A decision is then made about whether to persist with stimulation of the present electrodes or move to the next. The patient is able to stop the study at any time.

The Testing Session

Not including the time to set-up equipment, the actual testing session is expected to last \sim 1-2 hour and will not exceed four hours. The patient can take breaks during the session for food, rest, drink or bathroom use. The patient is at liberty to terminate the session at any time. Brain stimulation will be performed as detailed above.

Number of Sessions

Patients will undergo three ~1-2-hour testing sessions occurring on subsequent days.

Debriefing

The patient will be given the opportunity to ask questions of the team at any time, but will be invited to do so at the end of a session. This way, they can learn about what was tested and how this knowledge can lead to better patient outcomes or increased knowledge of brain function. We will not give medical advice during this de-brief and the study is not designed to provide information that is useful in relate to a specific patient's care. Where there is such information, this will be relayed to the clinical team.

Data and Specimen Banking

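### The safety threshold test is counted for five combinations but lists seven (84 patterns, not 60), one grid dimension is misprinted, and neither maximum-current rule gives a number when no effect is seen by 3.0 mA

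*Combined protocol and SAP*

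**What the plan says.** **Count and time.** Under Pre-stimulation threshold testing, the procedure opens with "Seven stimulation frequency pulse-width combinations will be tested" and lists seven pairs. Each starts at 0.25 mA and rises in 0.25 mA steps until a side-effect, an unwanted LFP change, or 3.0 mA. The same section then states: "This limits the number of tests to 5 frequency/pulse width combinations at 12 current amplitudes, for a maximum total of 60 stimulation patterns". Each pattern takes 60 seconds (5 s on and 15 s off, three times), and "The total test time will be approximately 60 minutes". The Testing Session gives a session length of "1-2 hour and will not exceed four hours".

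**Grid.** Parameter search sets out 35 currents (0.1-3.5 mA), 124 frequencies (2-125 Hz) and a third line, "Pulse width 100-450" μs in steps of 10, labelled as 35 values. The result is an "input space consisting of a maximum 156,240 potential stimulation patterns". From this total the plan takes out any pattern that threshold testing shows to be unsafe and any that the equipment cannot deliver. Footnotes say that the top current comes from threshold testing and that the top pulse width depends on frequency.

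**Maximum current.** Two rules appear.
- Intracranial stimulation protocol: find the afterdischarge threshold (anticipated at 0.2-2 mA) and go 25% below it. This holds for the whole of testing and is not tied to a frequency/pulse-width pair.
- Pre-stimulation threshold testing: for each combination, 80% of the current that produced a side-effect or unwanted LFP change.

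Parameter search also bars settings outside the identified thresholds, in its description of the data-driven optimisation algorithm.

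**The concern.** The figure of 60 is offered as the upper limit on the patterns a patient receives in safety testing, and the one-hour duration goes with it. If the list of seven is what will be run, both understate the planned exposure. The seven and the five both stand in the current text, so this is a live contradiction. The revision table, which records the "addition of 2 new stimulation frequency pulsewidth combinations for safety threshold testing", only suggests how it arose.

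The grid misprint matters less, but a reader multiplying the three printed dimensions will not reach the printed total.

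The current limits matter for a different reason. The protocol itself names reaching 3.0 mA as one way a staircase can end. If it ends there with no effect, an operator looking for the maximum to use in later sweeps finds two rules, neither of which returns a value, and a footnote that gives no derivation. Two operators could set different limits from the same threshold data.

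**Working it through.** **1. Threshold-test count.** Inputs from Pre-stimulation threshold testing.
- Amplitudes: 3.0 / 0.25 = 12.
- The plan's figure: 5 x 12 = 60 patterns; 60 x 60 s = 60 min. It reproduces only with five combinations.
- Trains: 60 x 3 = 180; on-time 180 x 5 s = 15 min.
- With the seven listed: 7 x 12 = 84 patterns; 84 x 3 = 252 trains; on-time 252 x 5 s = 21 min; total 84 x 60 s = 84 min.
- Difference: 24 patterns; 84 / 60 = 1.40, or 40% more.
- Optional longer trains at low frequency: if 2 and 7 Hz use 10-15 s trains and washout stays at 15 s (an assumption), the addition is 2 x 12 x 3 = 72 trains x 5-10 s = 6-12 min. The total becomes 90-96 min.

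**2. Grid total.** Inputs from Parameter search.
- Pulse widths, endpoints included: (450 - 100) / 10 + 1 = 36.
- 35 x 124 x 36 = 156,240, which matches the plan exactly.
- 35 x 124 x 35 = 151,900 with the printed label. The total is right; the label is wrong.

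**3. Maximum current when nothing is observed by 3.0 mA.**
- The 80% rule needs an effect current. There is none, so there is no value.
- The 25% rule needs an afterdischarge threshold. There is none, so there is no value.
- The grid is printed to 3.5 mA. Nominally, 5 of 35 current levels, or 5 / 35 = 14.3% of patterns, lie above 3.0 mA. This share describes the printed grid before any threshold, hardware or pulse-width exclusion.
- Charge density, reading the printed contact area as 0.059 cm² (an assumption): 3.5 mA x 450 μs = 1.575 μC; 1.575 / 0.059 = 26.7 against the limit of 30 μC/cm²/phase. The limit would bind for contacts smaller than 1.575 / 30 = 0.0525 cm². Whether it closes the gap therefore depends on the contact.

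**4. Pairs not tested.** The nominal grid has 124 x 36 = 4,464 frequency/pulse-width pairs, of which the staircase lists 7. The pulse-width footnote will reduce the 4,464. The 80% rule is set per combination, and no step carries it to other pairs. The 25% rule covers the whole patient, but only once an afterdischarge threshold has been found.

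**5. The two rules compared.** Take an afterdischarge at 2.0 mA, and suppose it counts as an unwanted LFP change. The 25% rule gives 2.0 x 0.75 = 1.5 mA; the 80% rule gives 2.0 x 0.80 = 1.6 mA. The text does not say which governs.

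**The case against.** On the count, the best defence is that 84 is a ceiling seldom reached: a combination stops as soon as an effect appears, and even 84 to 96 minutes fits the stated session. That is true and limits the consequence. It does not rescue the figure, because 60 is itself presented as the ceiling.

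On maximum current the objections carry more weight, and three stronger readings should be set aside.

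- A reader might infer that untested pairs have no threshold-derived limit at all. The documents do not support this. The limit of 25% below afterdischarge threshold is patient-wide and covers every pair once that threshold is known. The gap is left for patients without one.
- A reader might infer that about one sweep stimulation in seven will exceed 3.0 mA. This does not follow either. The 3.5 mA carries a footnote making it subject to threshold results, and the first session is meant to establish the safe range for later sweeps. A natural reading keeps the sweep inside what was tested. The 14.3% describes a printed grid, not planned exposure.
- A reader might infer that nothing else protects such a patient. In fact the EEG is watched throughout every session. An afterdischarge halts testing and lowers the current, and a recurrence or an elicited clinical seizure ends testing. Stimulation also stops if the patient notices anything. These rules apply in full, though they react to events and set no maximum in advance.

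The anticipated afterdischarge range of 0.2-2 mA lies wholly below 3.0 mA, so the no-effect outcome is likely to be uncommon. Clinicians may also test further settings or choose lower limits, but the text does not require either.

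What stands is that the protocol provides for a staircase ending without an effect and gives no maximum for that ending. The bar on exceeding identified thresholds is written for the optimisation algorithm; the default random sweep has no matching sentence.

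**Conclusion.** Three findings of unequal weight.

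- **Count and time: wrong as written.** The maximum for the listed procedure is 84 patterns and about 84 minutes, not 60 and about 60. This is certain if all seven combinations are run, and it is an upper bound.
- **Pulse-width count: a minor label error.** It should read 36; the grid total needs no change.
- **Maximum current: a narrow gap and an unreconciled pair of rules.** No maximum is defined when 3.0 mA is reached without effect. The 80% rule does not reach untested pairs, and the 25% rule does so only after an afterdischarge. Where both apply they can differ, as in the 1.5 against 1.6 mA example. How many patients would show no effect is not given, and the protocol's own anticipated range suggests few.

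The grid-share and charge-density figures are nominal: they precede the frequency-dependent pulse-width limit, and the charge-density figure also assumes a 0.059 cm² contact. This should be fixed; it does not show that patients would be stimulated beyond a safe level.

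**What to change.** - In Pre-stimulation threshold testing, restate the maximum for the seven listed combinations (84 patterns, 252 trains, about 84 minutes, longer with the optional low-frequency trains), or reconcile the list with the count of five.
- In Parameter search, correct the pulse-width count to 36 and leave the total alone.
- Reconcile the maximum-current text across Intracranial stimulation protocol, Pre-stimulation threshold testing and Parameter search. It should cover a staircase that ends at 3.0 mA without effect and pairs that were not tested, state which of the two rules governs when both apply, and say whether the bar written for the optimisation algorithm also binds the random sweep. The choice of rules belongs to the clinical team.

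The cost is amendment wording, with no added patients or procedures. The downside is that the stated exposure and first-session time become slightly less favourable.

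### On a 0.25 mA ladder, the 80% rule lets the sweep maximum exceed the last tolerated current when side-effects or non-afterdischarge LFP changes first appear at 0.50, 0.75 or 1.00 mA (minor)

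*Combined protocol and SAP*

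**What the plan says.** All references are to the combined protocol and SAP, Study Design and Methods.

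- **Purpose of the first session** (Pre-stimulation threshold testing): to "establish the range of safe stimulation parameters that can be tested in subsequent parameter sweeps".
- **Ladder** (same section): "Each frequency/pulse width combination will be tested at 0.25 mA, and incremented by 0.25 mA". It stops at a side-effect, an undesired LFP change or 3.0 mA, which gives 12 amplitudes for each combination.
- **Sweep maximum** (same section): "the maximum current threshold for each frequency/pulse width combination will be set to 80% of the current that induced patient-reported side-effects", or that induced undesired LFP changes.
- **Afterdischarge maximum** (Intracranial stimulation protocol, before the ladder is described): current is raised stepwise to "identify the threshold for afterdischarge (anticipated range 0.2-2 mA", and then "decreased by 25% for the maximum amplitude for the duration of testing".
- **Halt rule** (Pre-stimulation threshold testing, stated for all sessions): after an afterdischarge has stopped, "stimulation current will be decreased by 25-30% and testing will resume". "If afterdischarges occur again, all testing will be aborted on the patient".
- **Sweep grid** (Parameter search): current is discretised as "mA with 0.1 mA increments (35 values", with its upper limit taken from the threshold tests. Patterns identified as unsafe are removed. The optional optimisation search is held to the same thresholds.
- **Discretion** (Pre-stimulation threshold testing): the clinician may test further settings within the safety limit, and the neurologist may set lower limits.

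**The concern.** The ladder locates the true threshold only to within one step: above the last tolerated current and at or below the inducing one. A 20% reduction from the inducing current is narrower than one 0.25 mA step whenever the inducing current is below 1.25 mA. In those patients the sweep may use currents that threshold testing never showed to be tolerated, although showing this is the purpose of the first session. Only patterns found unsafe are removed, so untested currents stay in the sweep, and the optimisation search inherits the same limit.

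What is at stake is an avoidable side-effect or LFP disturbance in a patient with a low threshold. Three of the 12 ladder steps are affected, and all three lie inside the 0.2-2 mA range anticipated for afterdischarges. The protocol anticipates no range for side-effects.

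**Working it through.** **Inputs.** Ladder start and step 0.25 mA, ceiling 3.0 mA, and 80% rule (Pre-stimulation threshold testing); 25% cut (Intracranial stimulation protocol); 0.1 mA grid, 180 non-repeated stimulations and 156,240 patterns (Parameter search).

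**The plan's own figure.** 3.0 / 0.25 = 12 amplitudes, as stated.

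**80% rule.** If the effect is first seen at current I, the last tolerated step is I - 0.25 and the maximum is 0.80 I. The maximum is higher when 0.80 I > I - 0.25, that is, when 0.20 I < 0.25, or I < 1.25 mA. For the 25% cut, 0.75 I > I - 0.25 gives I < 1.00 mA.

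| I (mA) | Last tolerated | 0.80 I | Excess | Grid currents above tolerated (80%) | 0.75 I, rounded down to grid |
|---|---|---|---|---|---|
| 0.25 | none | 0.20 | n/a | n/a | 0.1875 → 0.1 |
| 0.50 | 0.25 | 0.40 | 0.15 | 0.3, 0.4 | 0.375 → 0.3 |
| 0.75 | 0.50 | 0.60 | 0.10 | 0.6 | 0.5625 → 0.5 |
| 1.00 | 0.75 | 0.80 | 0.05 | 0.8 | 0.75 → 0.7 |
| 1.25 | 1.00 | 1.00 | 0 | none | 0.9375 → 0.9 |
| 1.50 | 1.25 | 1.20 | -0.05 | none | 1.125 → 1.1 |
| 3.00 | 2.75 | 2.40 | -0.35 | none | 2.25 → 2.2 |

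As ratios to the last tolerated current, the three excesses are 0.40/0.25 = 1.60, 0.60/0.50 = 1.20 and 0.80/0.75 = 1.07.

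**Afterdischarges under the 25% cut.** On the grid, only 0.3 mA at the 0.50 mA step lies above the tolerated 0.25 mA. At 0.75 mA the grid maximum (0.5) equals the tolerated current, and at 1.00 mA it is below it (0.7 against 0.75).

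**Effect of the halt rule on the ladder.** A 25-30% cut from 0.50 mA gives 0.35-0.375 mA. If testing resumes there on the same combination, either that current is tolerated, which covers 0.3 mA, or the afterdischarge recurs and all testing ends.

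**How often the sweep would land in the gap.** There are 156,240 / 35 = 4,464 frequency and pulse-width combinations. Assume uniform draws, all seven tested combinations failing at the same step, and every other combination bounded at the same maximum. The frequency-dependent limit on pulse width is ignored; it would reduce the number of combinations and raise these figures somewhat.

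- All fail at 0.50 mA: 4 × 4,464 = 17,856 patterns, of which 7 × 2 = 14 lie in the gap. Expected draws are 180 × 14 / 17,856 = 0.14 per sweep, or about a 13% chance of at least one.
- All fail at 0.75 mA: 180 × 7 / (6 × 4,464) = 0.05.
- All fail at 1.00 mA: 180 × 7 / (8 × 4,464) = 0.04.

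**The case against.** The strongest reply is that 80% of the inducing current is simply how the plan defines its safe range. It always leaves a 20% margin, and nowhere does the plan promise that each sweep current was itself tolerated. Safeguards surround it: live EEG with a halt rule, stopping when the patient reports anything, freedom to test intermediate currents, and optional lower limits. Each sweep pattern is given once for 5 seconds, whereas a ladder pattern is given three times. Within the seven tested combinations the expected number of gap draws is well below one per sweep. All of this stands and limits the importance of the point. It does not remove it: monitoring acts after the event, the discretionary steps are optional, and nothing caps the maximum.

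Two stronger readings are tempting, and the documents do not support them.

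- A reader might infer that the 80% and 25% rules conflict irreconcilably for afterdischarges. They do not. The 25% cut is specific to afterdischarges and stated for the duration of testing. It always gives a lower current than 80%, and lower limits are expressly allowed, so applying it breaches neither sentence. What remains is that the 80% sentence does not repeat it.
- A reader might infer that it is unclear whether an afterdischarge on the ladder counts as the first event under the halt rule. The rule sits in the threshold-testing section and covers all sessions and any afterdischarge, so on a plain reading it does count.

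**Conclusion.** The point holds, mainly for patient-reported side-effects and LFP changes other than afterdischarges. At three of 12 ladder steps the sweep maximum exceeds the last tolerated current, by 0.05 to 0.15 mA. For afterdischarges, if the 25% cut governs, one grid current (0.3 mA at the 0.50 mA step) remains, and resuming the ladder at 70-75% of the inducing current may test even that.

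This is a minor improvement in wording. The documents give no distribution of thresholds, so the share of patients affected cannot be stated, and no claim about participants lost from the 18 can be supported. The conclusion assumes that an afterdischarge is one kind of undesired LFP change, a term the plan does not define, and that no intermediate current was tested at the clinician's discretion. It covers only the seven tested combinations; how limits are assigned to other sweep combinations is a separate matter.

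**What to change.** Amend the 80% sentence in Pre-stimulation threshold testing. For each tested combination, set the sweep maximum at the lower of (a) 80% of the inducing current, or 75% if the trigger was an afterdischarge, in line with Intracranial stimulation protocol, and (b) the highest current actually tolerated at that combination. The wording of (b) gives credit for any intermediate current tested. If the effect occurs at the first 0.25 mA step, use the percentage alone (0.20 mA at 80%; 0.1 mA on the grid at 75%) and have the neurologist confirm tolerance before the sweep.

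The cost is one sentence and a few grid currents. At 80% with the cap, and no intermediate testing, the sweep loses 0.3 and 0.4 mA at the 0.50 mA step, 0.6 mA at 0.75 and 0.8 mA at 1.00. Nothing changes from 1.25 mA upward. For afterdischarges, 75% in place of 80% also lowers the grid maximum by 0.1 mA at steps from 1.25 to 2.00 mA (for example 0.9 instead of 1.0 at 1.25) and by 0.2 mA from 2.25 to 3.00 mA (2.2 instead of 2.4 at 3.00). The cap ensures that, where a tolerated current exists, no sweep current at a tested combination exceeds it. It does not guarantee a margin below the true threshold.
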